9.6. Clinical Laboratory Evaluations

Clinical safety laboratory parameters (WBC, Hgb, PLT, ALT, AST, T. Bili, GGT, ALP, Amylase, Lipase, Cr) will be collected from each subject prior to the first study vaccination and approximately 7 days the first study vaccination. These evaluations will be performed by the central clinical laboratory. The grading scale for clinical laboratory evaluations is presented in [Table 10](#). Clinical laboratory evaluations assessed on Day 1 prior to the first study vaccination will be considered as baseline.

The distribution of laboratory results by severity, study day and study arm will be presented starting with [Table 139](#) and ending with [Table 150](#). Descriptive statistics including mean, standard deviation, median, minimum and maximum values and change from baseline by study day will be summarized for each parameter starting with [Table 151](#) and ending with [Table 161](#). Box plots illustrating the change from baseline for each laboratory parameter will be presented starting with [Figure 102](#) and ending with [Figure 112](#). Subject visits with abnormal laboratory results, Grade 1 severity or higher, will be presented in [Table 162](#) and [Table 163](#) for Chemistry and Hematology parameters, respectively.

A complete listing of individual clinical laboratory results will be presented in [Listing 23](#) and [Listing 24](#) for chemistry and hematology, respectively, sorted by subject ID, parameter, and visit number.

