**Table 1: Study Objectives and Outcome Measures**

Primary Safety Objectives	Primary Safety Outcome Measures

 
To assess the safety and reactogenicity of 2018/2019 Fluzone and Flublok with and without AF03 or Advax-CpG55.2 adjuvant.
 
	
 
Occurrence of solicited injection site and systemic reactogenicity events through approximately Day 8 after the first study vaccination.
 
Occurrence of unsolicited adverse events from the time of the first study vaccination through approximately Day 29.
 
Occurrence of all SAEs through approximately 12 months following receipt of the first study vaccination.
 
Occurrence of abnormal clinical safety laboratory AEs from the time of study vaccination through approximately Day 8 after the first study vaccination.
 

Primary Immunogenicity Objectives	Primary Immunogenicity Outcome Measures

 
To assess the serum hemagglutination inhibition (HAI) antibody responses against 2018/2019 QIV strains from baseline (Day 1) to approximately Day 29 after receipt of 2018/2019 Fluzone and Flublok with and without AF03 or Advax-CpG55.2 adjuvant.
 
	
 
The percentage of subjects achieving HAI titer seroconversion against the 2018/2019 QIV strains (defined as either a pre-vaccination titer <1:10 and a post-vaccination titer ≥1:40 or a pre-vaccination titer ≥1:10 and a minimum four-fold rise in post-vaccination antibody titer) on approximately Day 29 for each study group.
 
The percentage of subjects with an HAI titer ≥1:40 against the 2018/2019 QIV strains at baseline and approximately Day 29 for each study group.
 
Geometric mean titers (GMTs) of serum HAI against the 2018/2019 QIV strains at baseline and approximately Day 29 for each study group.
 

	
 
• Ratio of GMTs of serum HAI against the 2018/2019 QIV strains between adjuvanted and unadjuvanted study groups at baseline and approximately Day 29.
 
• Geometric mean fold rise (GMFR) in HAI titers from baseline (Day 1) against the 2018/2019 QIV strains at approximately Day 29 for each study group
 

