#### **8.4 Early Termination Visit (if needed)**

The following activities will be performed at the Early Termination Visit on subjects who withdraw, or are withdrawn or terminated from this trial:

- Interim medical history, including an assessment for new medical conditions, stability of chronic diseases and symptoms suggestive of AESIs (including Protocol Specified AESIs, MAAEs, NOCMCs and PIMMCs), will be obtained by interview of subjects and any changes since the previous clinic visit will be noted.
- All concomitant medications will be recorded on the appropriate DCF (if prior to 28 days after the first study vaccination). Receipt of any non-study influenza vaccines will also be recorded on the appropriate DCF (if within 365 days after first study vaccination).
- All AE/SAEs will be recorded on the appropriate DCF. Unsolicited AEs (if occurs within 28 days of the first study vaccination). SAEs and AESIs (including Protocol Specified AESIs, MAAEs, NOCMCs and PIMMCs) that have occurred since the previous clinic visit will be solicited (if within 365 days after first study vaccination).
- Memory Aid information will be reviewed with subjects (if within 7 days after the first study vaccination).
- Vital signs, including oral temperature, pulse and BP, may be obtained if indicated. Subjects must not eat or drink anything hot or cold, or smoke within 10 minutes prior to taking oral temperature.
- A targeted physical examination, including an assessment for signs suggestive of AESIs (including Protocol Specified AESIs, MAAEs, NOCMCs and PIMMCs) may be performed, if indicated based on review of interim medical history, by a study clinician

licensed to make medical diagnoses and listed on the Form FDA 1572 as the site PI or sub-investigator.

- The study vaccination site will be examined (if within 7 days after the first study vaccination).
- Post administration reactogenicity assessment will be performed (if within 7 days after the first study vaccination).
- Approximately 6 mL of venous blood will be collected for clinical safety labs (WBC, Hgb, PLT, ALT, T. Bili, AST, GGT, ALP, serum lipase and amylase and Cr) to be performed by the Central Clinical Laboratory (if within 7 days after the first study vaccination).
- Approximately 20 mL of venous blood will be collected for serological assays.
- Approximately 80 mL of venous blood will be collected for cellular immunology assays (if prior to or at the Day 90 visit).

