## **8.5      **Unscheduled Visit (if needed)****

An Unscheduled Visit may occur at any time during this trial. Any of the following activities may be performed:

- Interim medical history, including an assessment for new medical conditions, stability of chronic diseases and symptoms suggestive of AESIs (including Protocol Specified AESIs, MAAEs, NOCMCs and PIMMCs) will be obtained by interview of subjects and any changes since the previous clinic visit or phone call will be noted (if indicated).
- All concomitant medications will be recorded on the appropriate DCF (if within 28 days after first study vaccination). Receipt of any non-study influenza vaccines will also be recorded on the appropriate DCF (if within 365 days after first study vaccination).
- All AE/SAEs will be recorded on the appropriate DCF. Unsolicited AEs (if occurs within 28 days of the first study vaccination). SAEs and AESIs (including Protocol Specified AESIs, MAAEs, NOCMCs and PIMMCs) that have occurred since the previous clinic visit will be solicited (if within 365 days after first study vaccination).

- Memory Aid information will be reviewed with subjects (if within 7 days after the first study vaccination).
- Vital signs, including oral temperature, pulse and BP, may be obtained if indicated. Subjects must not eat or drink anything hot or cold, or smoke within 10 minutes prior to taking oral temperature.
- A targeted physical examination, including an assessment for signs suggestive of AESIs (including Protocol Specified AESIs, MAAEs, NOCMCs and PIMMCs), may be performed, if indicated based on review of interim medical history, by a study clinician licensed to make medical diagnoses and listed on the Form FDA 1572 as the site PI or sub-investigator.
- The study vaccination site will be examined (if within 7 days after study vaccination).
- Post administration reactogenicity assessment will be performed (if within 7 days after the first study vaccination).
- Site investigators have the discretion of administering 2019/2020 Fluzone or Flublok QIV earlier than the Day 90 window (i.e. earlier than Day 76) if 10% or more of surveillance samples in the CDC geographic region surrounding the local site test positive for influenza.
- Approximately 6 mL of venous blood will be collected for clinical safety labs (WBC, Hgb, PLT, ALT, T. Bili, AST, GGT, ALP serum lipase and amylase and Cr) to be performed by the Central Clinical Laboratory (if indicated).

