### **11.6.2 Safety Data**

Summaries and analysis of safety data will be presented for the Safety Analysis Population. All summaries and analyses will be presented for all subjects.

Solicited AEs will be summarized by severity after the first study vaccination (1-7 days post study vaccination) and as the maximum severity over all 8 days. Additionally, solicited AEs will be analyzed by taking the most severe response over the follow-up period, dichotomizing into a binary variable (none versus mild, moderate, or severe) and using standard techniques, such as exact confidence intervals, to summarize the proportion of subjects reporting each symptom, any injection site symptom, and any systemic symptom. Summaries of solicited AEs will be presented for the first study vaccination by treatment arm. The proportion of subjects reporting symptoms may be compared between treatment arms using Chi-square or Fisher's exact test. Unsolicited AEs will be coded by Medical Dictionary for Regulatory Activities (MedDRA®) for preferred term and system organ class (SOC). The numbers of SAEs and AESIs (including Protocol Specified AESIs, MAAEs, NOCMCs and PIMMCs) are likely to be small in this trial and will be reported by detailed listings showing the event description, MedDRA® preferred term and SOC, relevant dates (study vaccinations and AEs), severity, relatedness, and outcome for each event. Non-serious unsolicited AEs will be summarized as number and percentage of subjects reporting at least one event in each MedDRA® preferred term and SOC, cross tabulated by severity and relationship to study product. Additionally, the proportion of subjects and exact 95% confidence intervals of AEs in aggregate and by MedDRA® categories will be computed. Clinical laboratory data will be summarized by severity for each visit and as the maximum over all post-study vaccination visits. Graphical presentations may include box plots.

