12. SUMMARY OF CHANGES IN THE CONDUCT OF THE STUDY OR PLANNED ANALYSES

This SAP includes one change from the analyses described in the protocol. Logistic regression will be used instead of the Chi-Square or Fisher's exact test to model the relationship of treatment with reporting any local or systemic events post vaccination. Besides providing the strength of the association between the treatment and probability of reporting any local or systemic event in terms of odds ratio, logistic regression also provides a prediction model for the probability of a local or solicited event occurring given the subject's study arm. Version 3.0 of the SAP includes moving Day 180 and Day 365 immunogenicity endpoints from secondary to exploratory endpoints and the addition of a topline report.

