14.3.4 Displays of Laboratory Results

Table 139: Laboratory Results by Parameter, Maximum Severity, Study Day, and Study Arm – All Laboratory Parameters*

Study Arm	Study Day	N	None		Mild/ Grade 1		Moderate/ Grade 2		Severe/ Grade 3		Missing	
			n	%	n	%	n	%	n	%	n	%
Group 1: Fluzone (N=X)	Baseline	x	x	xx	x	xx	x	xx	x	xx	x	xx
	Day 8	x	x	xx	x	xx	x	xx	x	xx	x	xx
Group 2: Fluzone + AF03 (N=X)	Baseline	x	x	xx	x	xx	x	xx	x	xx	x	xx
	Day 8	x	x	xx	x	xx	x	xx	x	xx	x	xx
Group 3: Fluzone + Advax-CpG (N=X)	Baseline	x	x	xx	x	xx	x	xx	x	xx	x	xx
	Day 8	x	x	xx	x	xx	x	xx	x	xx	x	xx
Group 4: Flublok (N=X)	Baseline	x	x	xx	x	xx	x	xx	x	xx	x	xx
	Day 8	x	x	xx	x	xx	x	xx	x	xx	x	xx
Group 5: Flublok + AF03 (N=X)	Baseline	x	x	xx	x	xx	x	xx	x	xx	x	xx
	Day 8	x	x	xx	x	xx	x	xx	x	xx	x	xx
Group 6: Flublok + Advax-CpG (N=X)	Baseline	x	x	xx	x	xx	x	xx	x	xx	x	xx
	Day 8	x	x	xx	x	xx	x	xx	x	xx	x	xx

N = Number of subjects in the Safety Population.

Table 140: Laboratory Results by Parameter, Maximum Severity, Study Day, and Study Arm – White Blood Cells

Study Arm	Study Day	N	None		Mild/ Grade 1 (Low)		Mild/ Grade 1 (High)		Moderate/ Grade 2 (Low)		Moderate/ Grade 2 (High)		Severe/ Grade 3 (Low)		Severe/ Grade 3 (High)		Missing	
			n	%	n	%	n	%	n	%	n	%	n	%	n	%	n	%
Group 1: Fluzone (N=X)	Baseline	x	x	xx	x	xx	x	xx	x	xx	x	xx	x	xx	x	xx	x	xx
	Day 8	x	x	xx	x	xx	x	xx	x	xx	x	xx	x	xx	x	xx	x	xx
Group 2: Fluzone + AF03 (N=X)	Baseline	x	x	xx	x	xx	x	xx	x	xx	x	xx	x	xx	x	xx	x	xx
	Day 8	x	x	xx	x	xx	x	xx	x	xx	x	xx	x	xx	x	xx	x	xx
Group 3: Fluzone + Advax-CpG (N=X)	Baseline	x	x	xx	x	xx	x	xx	x	xx	x	xx	x	xx	x	xx	x	xx
	Day 8	x	x	xx	x	xx	x	xx	x	xx	x	xx	x	xx	x	xx	x	xx
Group 4: Flublok (N=X)	Baseline	x	x	xx	x	xx	x	xx	x	xx	x	xx	x	xx	x	xx	x	xx
	Day 8	x	x	xx	x	xx	x	xx	x	xx	x	xx	x	xx	x	xx	x	xx
Group 5: Flublok + AF03 (N=X)	Baseline	x	x	xx	x	xx	x	xx	x	xx	x	xx	x	xx	x	xx	x	xx
	Day 8	x	x	xx	x	xx	x	xx	x	xx	x	xx	x	xx	x	xx	x	xx
Group 6: Flublok + Advax-CpG (N=X)	Baseline	x	x	xx	x	xx	x	xx	x	xx	x	xx	x	xx	x	xx	x	xx
	Day 8	x	x	xx	x	xx	x	xx	x	xx	x	xx	x	xx	x	xx	x	xx

Note: N = Number of subjects in the Safety Population.

Tables with similar format:

Table 141: Laboratory Results by Parameter, Maximum Severity, Study Day, and Study Arm – Hemoglobin

Table 142: Laboratory Results by Parameter, Maximum Severity, Study Day, and Study Arm – Platelets

Table 143: Laboratory Results by Parameter, Maximum Severity, Study Day, and Study Arm – Alanine Aminotransferase (ALT)

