14.3.6 Displays of Vital Signs

Table 164: Vital Signs by Assessment, Maximum Severity, Time Point, and Study Arm – Any Assessment

Study Arm	Study Day	N	None		Mild		Moderate		Severe		Missing	
			n	%	n	%	n	%	n	%	n	%
Group 1: Fluzone (N=X)	Baseline	x	x	xx	x	xx	x	xx	x	xx	x	xx
	Max Severity Post Baseline	x	x	xx	x	xx	x	xx	x	xx	x	xx
Group 2: Fluzone + AF03 (N=X)	Baseline	x	x	xx	x	xx	x	xx	x	xx	x	xx
	Max Severity Post Baseline	x	x	xx	x	xx	x	xx	x	xx	x	xx
Group 3: Fluzone + Advax-CpG (N=X)	Baseline	x	x	xx	x	xx	x	xx	x	xx	x	xx
	Max Severity Post Baseline	x	x	xx	x	xx	x	xx	x	xx	x	xx
Group 4: Flublok (N=X)	Baseline	x	x	xx	x	xx	x	xx	x	xx	x	xx
	Max Severity Post Baseline	x	x	xx	x	xx	x	xx	x	xx	x	xx
Group 5: Flublok + AF03 (N=X)	Baseline	x	x	xx	x	xx	x	xx	x	xx	x	xx
	Max Severity Post Baseline	x	x	xx	x	xx	x	xx	x	xx	x	xx
Group 6: Flublok + Advax-CpG (N=X)	Baseline	x	x	xx	x	xx	x	xx	x	xx	x	xx
	Max Severity Post Baseline	x	x	xx	x	xx	x	xx	x	xx	x	xx

Note: The “Max Post Baseline” rows indicate the maximum severity experienced by each subject at any time point post baseline, including unscheduled assessments.
N= Number of subjects in the Safety Population

Table with similar format

Table 165: Vital Signs by Assessment, Maximum Severity, Time Point, and Study Arm – Oral Temperature

Table 166: Vital Signs by Assessment, Maximum Severity, Study Day, and Study Arm – Systolic Blood Pressure

Study Arm	Study Day	N	None		Mild (Low)		Mild (High)		Moderate (Low)		Moderate (High)		Severe (Low)		Severe (High)		Missing	
			n	%	n	%	n	%	n	%	n	%	n	%	n	%	n	%
			Group 1: Fluzone (N=X)	Baseline	x	x	xx	x	xx	x	xx	x	xx	x	xx	x	xx	x
	Max Severity Post Baseline	x	x	xx	x	xx	x	xx	x	xx	x	xx	x	xx	x	xx	x	xx
Group 2: Fluzone + AF03 (N=X)	Baseline	x	x	xx	x	xx	x	xx	x	xx	x	xx	x	xx	x	xx	x	xx
	Max Severity Post Baseline	x	x	xx	x	xx	x	xx	x	xx	x	xx	x	xx	x	xx	x	xx
Group 3: Fluzone + Advax-CpG (N=X)	Baseline	x	x	xx	x	xx	x	xx	x	xx	x	xx	x	xx	x	xx	x	xx
	Max Severity Post Baseline	x	x	xx	x	xx	x	xx	x	xx	x	xx	x	xx	x	xx	x	xx
Group 4: Flublok (N=X)	Baseline	x	x	xx	x	xx	x	xx	x	xx	x	xx	x	xx	x	xx	x	xx
	Max Severity Post Baseline	x	x	xx	x	xx	x	xx	x	xx	x	xx	x	xx	x	xx	x	xx
Group 5: Flublok + AF03 (N=X)	Baseline	x	x	xx	x	xx	x	xx	x	xx	x	xx	x	xx	x	xx	x	xx
	Max Severity Post Baseline	x	x	xx	x	xx	x	xx	x	xx	x	xx	x	xx	x	xx	x	xx
Group 6: Flublok + Advax-CpG (N=X)	Baseline	x	x	xx	x	xx	x	xx	x	xx	x	xx	x	xx	x	xx	x	xx
	Max Severity Post Baseline	x	x	xx	x	xx	x	xx	x	xx	x	xx	x	xx	x	xx	x	xx

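### The SAP laboratory severity tables (139–150) omit the protocol's maximum over all post-vaccination visits, without declaring it, so worse grades from off-schedule draws can be missing from the by-parameter counts by arm

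*SAP*

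**What the plan says.** Protocol 11.6.2 sets out two laboratory severity summaries: "Clinical laboratory data will be summarized by severity for each visit and as the maximum over all post-study vaccination visits".

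SAP 9.6 carries forward one of them: "The distribution of laboratory results by severity, study day and study arm will be presented starting with" Table 139 and ending with Table 150. The shells in SAP Appendix 1, 14.3.4 are titled "Laboratory Results by Parameter, Maximum Severity, Study Day, and Study Arm", but each arm has two rows only, Baseline and Day 8, with a Missing column. Table 139 pools all parameters, Table 140 is white blood cells, and Tables 141–150 follow the same format for the other ten parameters.

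The outcome concerned is a primary safety outcome in Protocol Table 1: "Occurrence of abnormal clinical safety laboratory AEs from the time of study vaccination through approximately Day 8 after the first study vaccination".

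SAP Section 12 opens with "This SAP includes one change from the analyses described in the protocol". That change is logistic regression for solicited events. The section then mentions the version 3.0 move of the Day 180 and Day 365 endpoints and the topline report. Laboratory summaries do not appear.

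**The concern.** The protocol maximum would repeat the Day 8 row only if Day 8 were the sole post-vaccination draw. It need not be. Protocol 8.5 allows safety laboratories at an unscheduled visit if indicated. Protocol 8.4 takes them at early termination within 7 days of the first vaccination. SAP Table 2 shows both. SAP 9.6 gives no rule that assigns these draws to a row.

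A subject with a worse grade at an unscheduled draw than at Day 8 therefore has no cell for that grade in Tables 139–150. Unscheduled draws are made when indicated, so they are not a neutral sample of results.

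The by-parameter, by-arm view has some interest here. Protocol 2.3.1 reports exocrine pancreas findings in rabbits at high adjuvant doses, judged there not clinically significant, and amylase and lipase are among the safety laboratories. Worst amylase and lipase grade by arm is the summary that would speak to this, and no planned table gives it across all draws.

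**Working it through.** No stated figure is at issue, so the check sets the texts side by side.

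**1. What each document plans**

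| Item | By visit | Maximum over post-vaccination visits |
|---|---|---|
| Protocol 11.6.2 | yes | yes |
| SAP 9.6 text | yes | no |
| Shells, Tables 139–150 | Baseline, Day 8 | no row |
| SAP Section 12 | – | omission not declared |

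**2. When the two summaries differ.** After vaccination, safety laboratories are scheduled once, at Day 8 (Protocol 7.2.1, Table 3 and Appendix A). For a subject with a Day 8 result and no other draw, maximum grade = Day 8 grade. With extra draws, maximum grade = max(Day 8 grade, off-schedule grades), which is never below the Day 8 grade. Leaving out the extra draws can lower the reported worst grade and cannot raise it. A subject who terminates early with no Day 8 draw has only the early-termination result. The SAP does not say whether that fills the Day 8 row or leaves the subject in the Missing column.

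**3. Where off-schedule results do appear**

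- Listings 23–24: all results, scheduled and unscheduled, by subject.
- Tables 162–163: results of Grade 1 or higher, by subject, with arm, parameter, severity and actual study day.
- Table 117: subjects with at least one laboratory AE, by grade and arm, with parameters pooled and no statement of which draws count.

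None of these gives counts by parameter and arm. In the expedited report, only the asterisked tables are planned. Tables 117 and 139 carry the mark; Tables 140–150 and 162–163 do not. The laboratory severity table in that report is therefore the pooled Baseline and Day 8 shell.

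**4. Window.** Unscheduled visits may occur at any time in the trial (Protocol 8.5), so to about Day 365 and after the Day 90 vaccine. Laboratory AEs are reported only to about 7 days after the first vaccination (Protocol 9.1, 9.3). A maximum over all draws and the primary outcome are thus two different quantities.

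**5. Scale, for illustration.** With 40 per arm, one subject is 1/40 = 2.5 percentage points. The exact two-sided 95% upper limit for 0/40 is 1 − 0.025^(1/40) = 8.8%; for 1/40 the Clopper–Pearson upper limit is 13.2%. Tables 139–150 show counts and percentages without intervals, so no planned output would move between these limits. The documents do not give the number of off-schedule draws, so the total effect cannot be computed.

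**The case against.** The strongest reply is that the omission is nearly harmless by design. With one scheduled post-vaccination laboratory visit, the Day 8 grade is already the maximum for every subject without an off-schedule draw. This stands, and it limits the size of the point.

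Four stronger readings are tempting and should be resisted.

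- *That the worst cases are hidden.* They are not. The listings hold them, and Table 117 is not restricted to scheduled visits. What is missing is the count by parameter and arm.
- *That a Grade 3 value on Day 3 falling to Grade 1 by Day 8 will be tabulated as Grade 1, or that an early terminator will be tabulated as Missing.* Both assume a visit-mapping rule that the SAP does not contain. A programmer could place an early-termination draw in the Day 8 row. These are possible results, not planned ones.
- *That the SAP treats laboratories and vital signs inconsistently.* The vital-sign shells (Tables 164–168) do have a post-baseline row, with a note that such "rows indicate the maximum severity experienced by each subject at any time point post baseline, including unscheduled assessments". But vital signs have no scheduled post-baseline assessment, so that row is the only way to show any. The comparison shows that a suitable layout exists, not that laboratories were handled carelessly.
- *That the maximum over all draws should also define the primary outcome.* It should not. It would bring results from months later, after a second vaccine, into an outcome that ends at about Day 8.

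None of this removes the mismatch. The protocol asks for the summary, the SAP drops it, and Section 12 does not say so.

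**Conclusion.** The point holds as an undeclared protocol–SAP mismatch that should be corrected. For a subject with a Day 8 result, following the SAP shells can only understate worst grade by parameter and arm. For early terminators the handling is undefined.

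The numerical effect is confined to subjects with off-schedule draws and is probably small: 2.5 percentage points of an arm per affected subject, with the number of such subjects unknown. The conclusion assumes that the Day 8 row is filled from the scheduled visit, which is the natural reading of the shells but is not stated. The documents do not support a claim that laboratory results are lost or that the primary outcome will be misreported. Only unscheduled draws up to about Day 8 and early-termination draws within 7 days bear on the primary outcome. Later unscheduled draws bear only on the wider summary in Protocol 11.6.2.

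**What to change.** - Add a 'Max Severity Post Baseline' row to each of Tables 139–150, taken over scheduled, unscheduled and early-termination draws, as Protocol 11.6.2 states. The layout and note of Table 164 can be reused, with early-termination draws named.
- State in SAP 9.6 how off-schedule draws map to rows, in particular whether an early-termination draw may fill the Day 8 row.
- For the primary laboratory outcome and the laboratory row of Table 117, count all draws from the first vaccination through about Day 8 only. Keep later unscheduled draws separate from that outcome.
- If the sponsor prefers to keep the present shells, declare and justify the omission in SAP Section 12.

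The cost is one row per arm in 12 tables and a few sentences of SAP text. No new data are needed, since Listings 23–24 already draw on all the results.
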